### **Sample Size Justification**

Power Analyses from Research Plan:

(Aim 1) To test the hypothesis for Aim 1, a paired-sample diagnostic analysis (estimated sensitivities/specificities) for each screening measure relative to the criterion standard, Level 1 PSG) was

performed using the same sample of patients. Prevalence of sleep apnea (as determined by Level 1 PSG) was conservatively estimated to be 30% using investigators' published reports of 37-39% prevalence in acute rehabilitation TBI samples. A two-sided McNemar's test, assuming a significance level of  $\alpha = 0.05$ , will have at least 80% power to detect a difference in sensitivities of 20% between screening measures for a sample size of 237. The power of the test will increase if the prevalence is higher than 30% (e.g., a prevalence of 35% would yield 87% power with 237 subjects and only require 203 subjects for 80% power). Furthermore, a sample size of 237 will have at least 80% power to detect a difference of 20% in sensitivities between screening measures in detecting sleep apnea.

(Aim 2) To test the non-inferiority hypothesis of the portable device for diagnosing sleep apnea, the non-inferiority of SE and SP (relative to SEH = 0.9 and SPH = 0.6, each within  $\Delta = 0.1$ ) were jointly tested at the significance level of  $\alpha=0.05$  by estimating the cross-product of two one-sided  $1-\alpha^*$  confidence intervals; SEH and SPH were selected a priori and were considered sufficiently large to obviate the need Level 1 PSG. For the purposes of the clinical trial, the study was powered to demonstrate non-inferiority of Level 3 sleep studies relative to fixed values of sensitivity (SE) and specificity (SP). Minimum sample sizes of 83 and 153 patients achieved at least 80% power to detect non-inferiority of SE to 90% and SP to 60% with a non-inferiority limit of  $\Delta = 0.1$ , using one-sided exact tests each at a 5% level of significance. In total, 214 subjects were available for analysis which yields 83.9% and 98.8% power, respectively, when testing the non-inferiority of SE and SP each at a 2.53% level of significance and maintaining a 5% level of significance when testing SE and SP jointly.

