Using individual significance levels of  $\alpha_{SE} = \alpha_{SP} = \alpha^* = 0.0253$  ensures that the overall significance region of the joint test of both SE and SP simultaneously remains no greater than  $\alpha = 0.05$ . If the lower confidence limits (LCL) from both  $1 - \alpha^* = 94.9\%$  confidence intervals are strictly above 0.8 for SE and 0.5 for SP, then a claim of non-inferiority of the portable diagnostic test would be established. Analyses were conducted for each AHI cutoff score (Total AHI  $\geq 5$ ,  $\geq 15$ , and  $\geq 30$ ) for the overall sample and by subgroups. The non-inferiority thresholds were chosen based on a prior systematic review showing estimates of SEs and SP for AHI  $\geq 5$  were 0.96 (95% CI = 0.90, 0.98) and 0.76 (95% CI = 0.63, 0.85), respectively, across varying OSA prevalence rates. Based on the lower bounds of these 95% confidence intervals (rounded to the nearest 10th), 90% SE and 60% SP with a delta of 0.1 were selected for declaration of non-inferiority.

3. Pepe MS. *The statistical evaluation of medical tests for classification and prediction*. 2003; Oxford University Press, New York.

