
established in the TBIMS database and will be applied for this study (i.e., unknown, not applicable) and generated in missing data reports for discussion. As the primary hypotheses require complete data from each subject (STOPBang, ACG, Level 1 PSG, and Level 3 PSG) all efforts will be made to minimize missing data from these key variables. For example, a patient may need to repeat PSG if it was not adequately captured. Any reasons for missing data will be recorded for each patient for a global sensitivity analyses to examine the effect of missingness on the conclusions of the hypotheses tests. Missing data reports will be reviewed on a quarterly basis by staff at the NDSC as well as coordinators at each site. This study will be a multi-site, prospective observational study investigating the comparative effectiveness of sleep apnea screening (Aim 1) and diagnostic (Aim 2) measures. A total of 258 subjects will be recruited to allow for attrition and meet study goals. Initial analyses will be undertaken to inspect data for errors, inconsistencies, and incomplete information. This will include examining the distribution of the data (frequency tables, histograms, box-plots). Data anomalies that cannot be resolved will be examined by study staff for clarification and possible correction. During the verification process, we will correct any inaccuracies in data entry and track the changes in the data accordingly. Incomplete entries will also be rectified if the missing information is available. However, missing data are inevitable in any study. Given the novelty of this area, imputation methods for missing data will not be applied. Efforts to minimize missing data impacting analyses include 1) close monitoring of missing data in real time (missing data reports reviewed biweekly) and 2) repeat testing given the captive nature of the audience during inpatient rehabilitation. Serial attempt to capture data will be tracked and analyzed across key demographic and injury severity variables. We will also examine consent rates and attrition from time of consent to completion of diagnostic tests and illustrated with the use of the STARD diagram. Participants who drop-out vs. those who complete the study will be compared on the key demographic and injury severity variables (e.g., sex, race, severity measures) to determine if there are group differences. If differences are present, interpretations of all study results will be made in light of these differences. Data analysis will begin with a review of descriptive statistics for all major variables and all major subgroupings of variables in the data set.

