(Aim 2: Hypothesis 2.1): *Level 3 portable polysomnography with greater consumer accessibility will be equivalent (non-inferior) to the less accessible Level 1 polysomnography in determining presence of sleep apnea in TBI patients undergoing inpatient rehabilitation.* Justification of Assumptions/Power Estimate: To test hypothesis 2.1, the sensitivity (SE) and specificity (SP) of Level 3 PSG (compared to Level 1 PSG, the reference gold standard) will each be estimated and compared to fixed hypothesized rates of SE and SP considered sufficiently large enough to potentially obviate the need for Level 1 PSG. Based on a review of the literature and consensus among the investigators in this study, SE and SP no worse (non-inferior) to 90% and 60%, respectively, are considered sufficiently large enough. To test for non-inferiority of the SE to 90% and the SP to 60%, a non-inferiority threshold of $\Delta = 0.1$ is assumed for both measures. A sample size of at least 83 patients is necessary to achieve a minimum of 80% power to test the non-inferiority of the SE to 90% (assuming $\Delta = 0.1$ and $\alpha = 0.05$). A sample size of at least 153 patients is necessary for a minimum of 80% power to test the non-inferiority of the SP to 60% (assuming $\Delta = 0.1$ and $\alpha = 0.05$). Thus, a total of 153 subjects is required to sufficiently power both non-inferiority hypotheses. Analytic Plan: To test hypothesis 2.1, the sensitivity (SE) and specificity (SP) of Level 3 PSG (compared to Level 1 PSG, the reference gold standard) will each be estimated and compared to fixed hypothesized rates of SE and SP of 90% and 60%, respectively, considered sufficiently large enough. Level 1 PSG (reference) diagnosis of sleep apnea will be made based on $AHI \geq 5$. Level 3 PSG (test) diagnosis will be made based $AHI \geq 5$. A cross-tabulation of Level 3 PSG (positive/negative) versus Level 1 PSG (positive/negative) will be constructed and standard measures of diagnostic accuracy will be estimated along with 95% confidence intervals (i.e., sensitivity, specificity, positive and negative predictive values, and diagnostic accuracy). To test for non-inferiority of the SE to 90% and the SP to 60%, a non-inferiority threshold of 0.1 is assumed. If the lower bound on the 95% confidence interval for SE is strictly above 80% and the lower bound on the confidence interval for SP is strictly above 50% then non-inferiority of Level 3 PSG (compared to Level 3 PSG) can be established. All analyses will be performed using SAS v.9.4 (SAS Institute Inc., Cary, NC).

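### Aim 2 power counts all 214 subjects in both the sensitivity and the specificity test and prints the two results in reverse; at the plan's 0.90/0.60, no split of 214 gives the stated pair

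*Protocol*

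**What the plan says.** The protocol (Sample Size Justification, Aim 2) tests sensitivity against 0.90 and specificity against 0.60, each with a margin of 0.1, so the null values are 0.80 and 0.50. It gives minimum sizes: "Minimum sample sizes of 83 and 153 patients achieved at least 80% power to detect non-inferiority of SE to 90% and SP to 60" per cent, "using one-sided exact tests each at a 5% level of significance". It then gives power for the analysed sample, with each test at 2.53%: "In total, 214 subjects were available for analysis which yields 83.9% and 98.8% power, respectively, when testing the non-inferiority of SE and SP".

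The SAP (Aim 2, Hypothesis 2.1, power estimate) has the same 83 and 153 and concludes: "Thus, a total of 153 subjects is required to sufficiently power both non-inferiority hypotheses". It defines disease status, for the reference and the portable test alike, by an AHI of 5 or more.

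Neither document gives a prevalence for Aim 2. For Aim 1 the protocol says: "Prevalence of sleep apnea (as determined by Level 1 PSG) was conservatively estimated to be 30" per cent, set against earlier reports of 37–39%.

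**The concern.** The denominator of sensitivity is the number of Level 1 PSG positives, and that of specificity is the number of negatives. The two groups share no patients, so 83 is a count of positives and 153 a count of negatives. Using 214 in both tests, or taking the larger of 83 and 153 as the total for both, counts every patient twice. The Aim 1 paragraph does let power for sensitivity depend on prevalence; Aim 2 does not.

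The printed order also looks wrong. At a common sample size, a test of 0.80 against 0.90 has more power than a test of 0.50 against 0.60, because the binomial variance is smaller. The documents' own minimum sizes say so: sensitivity needs 83 and specificity 153. Yet at 214 the protocol gives specificity the higher power.

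The non-inferiority claim requires both lower confidence limits to clear their bounds, so joint power is what matters. A reader weighing a failed specificity test would take it that such a failure was very unlikely if the true specificity were 0.60.

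**Working it through.** **Inputs.** Null and assumed true values: sensitivity 0.80 and 0.90, specificity 0.50 and 0.60. One-sided levels: 5% for the minimum sizes, 2.53% at 214 (protocol, Sample Size Justification). Prevalence: 30% and 37–39%, from the Aim 1 text.

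**Formulas** (one-sample normal approximation, p0 null, p1 true, q = 1 − p):

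- n = [(z_α√(p0q0) + z_β√(p1q1)) / (p1 − p0)]²
- power = Φ[(p1 − p0 − z_α√(p0q0/n)) / √(p1q1/n)]

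**1. Minimum sizes, 5% one-sided, 80% power.** With z_α = 1.645 and z_β = 0.842, n is 82.9 for sensitivity and 152.5 for specificity. Rounded up these are 83 and 153, the plan's numbers (power 80.06% and 80.13%).

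**2. Stated power, n = 214 in each test, 2.53% one-sided (z_α = 1.955).**

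- Sensitivity: (0.1 − 1.955 × 0.02734) / 0.02051 = 2.270, power 98.8%.
- Specificity: (0.1 − 1.955 × 0.03418) / 0.03349 = 0.991, power 83.9%.

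These are the two printed figures to the decimal, attached to the wrong parameters.

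**3. Can any split give the printed pair?** If all 214 were PSG-negative, specificity power would be 83.9% (83.2% exact). Reaching 98.8% needs about 434 negatives. This step uses no prevalence.

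**4. Power when 214 is divided by disease status, 2.53% each.** Joint power is the product, because the groups are separate patients.

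| Positives / negatives | Prevalence | Sensitivity | Specificity | Joint |
|---|---|---|---|---|
| 64 / 150 | 30% | 52% | 69% | 36% |
| 79 / 135 | 37% | 64% | 65% | 41% |
| 83 / 131 | 39% | 67% | 63% | 42% |
| 100 / 114 | 47% | 77% | 57% | 44% (maximum) |
| 107 / 107 | 50% | 80% | 55% | 44% |
| 117 / 97 | 55% | 84% | 51% | 43% |

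The printed pair multiplies to 0.839 × 0.988 = 0.829. Exact binomial tests over every split from 64/150 to 83/131 give sensitivity 47–70%, specificity 58–69% and joint 30–43%. The exact joint maximum over all splits is also about 44% (at 89/125).

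**5. The SAP total of 153, one-sided 5%.** At 30% prevalence (46/107), sensitivity power is 53% and specificity 67%. At 39% (60/93) they are 65% and 61%. Neither test reaches 80%.

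**6. Exact or approximate.** The protocol says exact tests. Exact power at one-sided 5% is 79.5% with 83 positives and 76.2% with 153 negatives, so the stated 80% minimum is met only by the approximation.

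**The case against.** Four points deserve weight.

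- **True accuracy may be better than 0.90/0.60.** The protocol took those values from lower confidence bounds; the review estimates themselves "were 0.96 (95% CI = 0.90, 0.98) and 0.76 (95% CI = 0.63, 0.85), respectively, across varying OSA prevalence rates". At true values of 0.96 and 0.76, exact joint power with 214 is 98–99.8% over the splits from 64/150 to 83/131. With a true sensitivity of 0.90 and a true specificity of 0.70 (a value the plan does not use), a 117/97 split gives 84.1% and 98.5%, close to the printed pair. So the impossibility is conditional on 0.90/0.60. It still stands as a criticism: those are the only values for which either document claims power, and the printed figures reproduce at them.
- **The prevalence is borrowed from Aim 1.** True, and it sets the 36–42% range. The reversal, the 83.9% ceiling for specificity and the 44% joint maximum do not depend on it.
- **Recruitment was not set at 153.** The SAP says: "A total of 258 subjects will be recruited to allow for attrition and meet study goals". A sample of 258 could hold both 83 positives and 153 negatives with 83 to 105 positives (32–41% prevalence), before attrition. But those sizes belong to 5% tests. At 2.53%, 80% power for each needs 107.0 positives and 193.1 negatives, about 301 or 302 in all depending on rounding.
- **The trial is complete and the decision rule does not use power.** This is correct and limits the consequence to interpretation. The protocol states no joint power either; the 83% is the product of its two figures.

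The exact-test discrepancy is minor beside the rest: half a point at 83 and about four points at 153.

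**Conclusion.** The concern holds. The Aim 2 power statement has the wrong denominators and its two results are interchanged, and the SAP's sufficient total of 153 is wrong for the same reason. The calculation behind the printed figures is inferred, since the protocol does not show it, but one formula reproduces all four numbers (83, 153, 98.8%, 83.9%).

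Assuming true sensitivity 0.90, true specificity 0.60 and 2.53% per test, the printed pair overstates joint power roughly twofold, at about 83% against a ceiling of 44%. Actual power cannot be given because the positive/negative split of the 214 is not in the documents. The data, the decision rule and any test result are unaffected. What is affected is the justification for 214 and the reading of a failure to show non-inferiority, above all for specificity.

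**What to change.** - In both documents, state that 83 is the number with AHI of 5 or more on Level 1 PSG and 153 the number without.
- In the SAP, delete the sentence that a total of 153 powers both hypotheses.
- In the protocol, replace the 83.9%/98.8% pair with correctly labelled sensitivity, specificity and joint power at the actual split of the 214, or over 30–39% prevalence if the split is not used. State the assumed true values of 0.90 and 0.60.
- Name one method, exact or normal approximation, and use it for both the minimum sizes and the achieved power.
- If 0.96/0.76 are regarded as the expected values, add power at those values as a separate, labelled scenario.

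The cost is recomputation and wording, and the stated power becomes less favourable. No added enrolment, new data or change to the decision rule is needed.

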#### Loss to follow-up:

See sample flow diagrams for each aim in corresponding publications.

### **Statistical Analysis Plan**

#### Primary Endpoint: (Aim 1) Receiver Operating Characteristic Area Under the Curve

To determine the predictive utility of the screening tools for diagnosing mild ( $AHI \geq 5$ ), moderate ( $AHI \geq 15$ ), and severe ( $AHI \geq 30$ ) sleep apnea, receiver-operating characteristics (ROC) curve analyses were performed. A ROC curve plots the true positive rate (sensitivity) against the false positive rate ( $1 - \text{specificity}$ ) for all possible cut-off scores of the screening tools. The area under the ROC curve (ROC AUC) and corresponding 95% confidence interval (CI) were estimated to provide a measure of overall discrimination for each screening tool. Standard diagnostic measures including sensitivity (SE), specificity (SP), positive predictive value (PPV) and negative predictive value (NPV), and false negative rate (FNR) were calculated across varying cut-off scores for each screening tool. The Youden index, commonly used to determine the optimal cut-off score where equal weight is given to sensitivity and specificity (defined as "sensitivity + specificity - 1" was also calculated). For MAPI probability, cut-off scores of 0.1 to 0.9 in increments of 0.1 were summarized along with the optimal cut-off score. For the Berlin, participants were either low risk (0 or 1 category positive) or high risk ( $\geq 2$  categories positive), so there is only one possible cut-off score. For Actigraphy, since less sleep is thought to be associated with worse sleep outcomes (such as sleep apnea), 12 hours minus the total sleep time was examined at 60-minute cut points from 3 to 10 hours. The ROC AUCs were compared among the four screening tools using a  $\chi^2$  test. Median with interquartile range (IQR) are provided.

(Aim 2) Sensitivity and Specificity Jointly Tested: To test the non-inferiority hypothesis of the portable device for diagnosing sleep apnea, the non-inferiority of SE and SP (relative to SEH = 0.9 and SPH = 0.6, each within  $\Delta = 0.1$ ) were jointly tested at the significance level of  $\alpha=0.05$  by estimating the cross-product of two one-sided  $1-\alpha^*$  confidence intervals; SEH and SPH were selected a priori and were considered sufficiently large to obviate the need Level 1 PSG.

Using individual significance levels of  $\alpha_{SE} = \alpha_{SP} = \alpha^* = 0.0253$  ensures that the overall significance region of the joint test of both SE and SP simultaneously remains no greater than  $\alpha = 0.05$ . If the lower confidence limits (LCL) from both  $1 - \alpha^* = 94.9\%$  confidence intervals are strictly above 0.8 for SE and 0.5 for SP, then a claim of non-inferiority of the portable diagnostic test would be established. Analyses were conducted for each AHI cutoff score (Total AHI  $\geq 5$ ,  $\geq 15$ , and  $\geq 30$ ) for the overall sample and by subgroups. The non-inferiority thresholds were chosen based on a prior systematic review showing estimates of SEs and SP for AHI  $\geq 5$  were 0.96 (95% CI = 0.90, 0.98) and 0.76 (95% CI = 0.63, 0.85), respectively, across varying OSA prevalence rates. Based on the lower bounds of these 95% confidence intervals (rounded to the nearest 10th), 90% SE and 60% SP with a delta of 0.1 were selected for declaration of non-inferiority.

3. Pepe MS. *The statistical evaluation of medical tests for classification and prediction*. 2003; Oxford University Press, New York.

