Exploratory Aim 2: Two new screening measures, MAPI and Berlin, have been used extensively as screening measures for sleep apnea in the general population, however little is known about their diagnostic capabilities in TBI patients undergoing inpatient rehabilitation. This study proposes to explore the diagnostic accuracy of these screening tools within this specific population. (ADD ANY OTHER DETAILS/JUSTIFICATION) Analytical Plan: Receiver operator curve (ROC) analyses will be conducted for MAPI and Berlin each. This will provide estimates of sensitivity and specificity for all possible cut-points on the MAPI and Berlin. Of particular interest is to identify sufficiently high sensitivity without compromising too much specificity (e.g., 90% SE and SP no smaller than 60%). All analyses will be performed using SAS v.9.4 (SAS Institute Inc., Cary, NC).

References

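### Accuracy at the data-selected (Youden) cut-offs in Aim 1 is too favourable on average, because the cut-off is chosen and assessed in the same patients without correction

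*Protocol*

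**What the plan says.** The Protocol's Statistical Analysis Plan (Primary Endpoint, Aim 1) estimates the ROC AUC of each screening tool at AHI thresholds of 5, 15 and 30. It also tabulates SE, SP, PPV, NPV and the false negative rate over a range of cut-offs. On choosing among them it says: "The Youden index, commonly used to determine the optimal cut-off score where equal weight is given to sensitivity and specificity". For MAPI, the cut-offs 0.1 to 0.9 in steps of 0.1 "were summarized along with the optimal cut-off score". Actigraphy is examined at hourly points from 3 to 10 hours, and the Berlin has a single cut-off.

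The SAP's Exploratory Aim 2 runs ROC analyses for MAPI and the Berlin over all cut-points. It adds: "Of particular interest is to identify sufficiently high sensitivity without compromising too much specificity", with 90% SE and SP of at least 60% as its example.

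The Protocol's Sample Size Justification says that the Aim 1 accuracy analysis was "performed using the same sample of patients". That phrase describes the pairing of tools, but neither document mentions a second sample. Neither mentions a split sample, cross-validation, a bootstrap or a validation cohort for the cut-offs.

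**The concern.** A cut-off that maximises the observed Youden index is partly chosen for chance error in its favour. Its observed SE and SP therefore tend to exceed what the same cut-off would achieve in new patients. A cut-off fixed beforehand has no such bias. The bias grows when the tool is weak, when one of the two groups is small (as cases may be at AHI 30 or above), and when more cut-offs are searched.

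What is at stake is the accuracy attached to any cut-off the plan calls optimal. The false negative rate is 1 − SE, so an SE that is 3 points too high is a missed-case rate 3 points too low, and that is the error that matters most for a screening tool.

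**Working it through.** **The plan's own figures.** The documents give no SE, SP or Youden index at an optimal cut-off, so there is no such figure to reproduce. The nearest is the Aim 1 power statement: "at least 80% power to detect a difference in sensitivities of 20% between screening measures for a sample size of 237". At 30% prevalence, 237 × 0.30 = 71 cases. An exact McNemar calculation returns 80.5% with 71 cases and 86.9% with 83 (237 × 0.35), if the discordant proportion is about 0.34. That proportion is not stated and was solved for. The power statement involves no cut-off search and is not in question here.

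**Inputs from the documents.**
- Aim 1 sample: 248 (Study Summary).
- Prevalence: "conservatively estimated to be 30% using investigators' published reports of 37-39% prevalence in acute rehabilitation TBI samples". This gives 248 × 0.30 = 74 cases and 174 non-cases.
- Cut-offs available: MAPI 9 grid points plus an optimum, which may lie off the grid; actigraphy 8 (3 to 10 hours); STOPBANG up to 8 (eight items); Berlin 1.

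**Assumptions not in the documents.** True AUC of 0.60, 0.70 or 0.80; equal-variance normal scores; equally spaced grids; 10% prevalence at a severe threshold, so 248 × 0.10 = 25 cases.

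**Method.** Non-cases score N(0,1) and cases N(d,1), with d = √2 × Φ⁻¹(AUC). At cut-off c the true values are SE = 1 − Φ(c − d), SP = Φ(c) and J = SE + SP − 1. In each simulated data set (4,000 or more per setting) the cut-off with the largest observed J is selected. The excess is observed J minus true J at that same cut-off, averaged over data sets.

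**Search over every observed value, 74 cases and 174 non-cases.**

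| True AUC | Apparent J | True J at that cut-off | Excess |
|---|---|---|---|
| 0.60 | 0.202 | 0.129 | 0.073 |
| 0.70 | 0.337 | 0.276 | 0.061 |
| 0.80 | 0.489 | 0.436 | 0.053 |

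At AUC 0.60 to 0.70 this is about 5 points of SE and 2 of SP.

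**Grid of 8 cut-offs, 30% prevalence.** At AUC 0.60 the excess is 0.029 in SE and 0.013 in SP, so 0.042 in J. At AUC 0.70 it is 0.020 and 0.008, so 0.028. Over AUC 0.60 to 0.80, 8 or 9 cut-offs and different spacings, the excess in J is about 0.02 to 0.05.

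**25 cases (assumed).** The excess in J is about 0.05 to 0.08 on the grid and 0.09 to 0.11 with a full search. The SP part is about 1 point or less, so nearly all of it is SE. Grid spacing and simulation error move the ends of these ranges by about 0.01.

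**Control.** At a cut-off fixed in advance, the mean error in SE and SP was about 0.1 point or less in every setting checked.

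**How far a bootstrap corrects this (74 and 174, full search).** At AUC 0.60 it moved J from 0.201 to 0.152 against a truth of 0.129: (0.201 − 0.152)/(0.201 − 0.129) = 68% of the bias removed. At AUC 0.70 it moved J from 0.336 to 0.293 against 0.276: 0.043/0.060 = 72%.

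**The case against.** The strongest reply is that no formal inference uses a selected cut-off. This stands. The Protocol's Aim 1 endpoint is "Receiver Operating Characteristic Area Under the Curve", compared across the four tools by a chi-square test. The SAP's Hypothesis 1.1 compares STOPBang and actigraphy by McNemar tests at cut-points fixed beforehand. A reader might infer that the comparison of tools is tilted towards those with more cut-offs and against the Berlin. The documents do not support that, because neither compares tools by their best Youden index. The tilt would arise only if someone set best-cut-off figures side by side.

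The search is also narrower than it may look. Only MAPI is explicitly given an optimal cut-off. For STOPBANG and actigraphy, selection is a fair inference from the general Youden sentence, but it is not stated. The Berlin offers nothing to select. SE and SP at the other listed cut-offs, each read as fixed, are not biased.

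The effect on a coarse grid is small beside sampling error. With 74 cases and SE of 0.70, the 95% half-width is 1.96 × √(0.70 × 0.30/74) = 0.10, against a bias of 2 to 3 points. This limits the importance of the point but does not answer it: a confidence interval computed as if the cut-off had been fixed carries the bias along and does not show it.

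Finally, a reader might take the plan to be recommending cut-offs to clinicians. Neither document says so. The Protocol calls a cut-off optimal, and the SAP's search is labelled exploratory.

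**Conclusion.** The point holds for data-selected cut-offs only: the optimal MAPI cut-off, any Youden optimum reported for STOPBANG or actigraphy, and any MAPI cut-point picked under the SAP's Exploratory Aim 2. On a grid of 8 or 9 cut-offs with 74 cases, the expected overstatement is about 2 to 3 points of SE and 1 of SP. It is larger for a freely searched MAPI and for a rare severe category.

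These sizes rest on the assumed AUCs, the binormal shape, the grid spacing and, for severe disease, the assumed 25 cases. They describe an average. It would go too far to say that SE and SP in this trial are overstated: with 8 cut-offs, both were too high together in only about 36% to 47% of simulated samples.

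The primary AUC and its chi-square comparison, the Berlin, the pre-set McNemar tests and Aim 2 stand as planned. This is a minor to moderate reporting weakness in secondary figures, and it is cheap to correct.

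**What to change.** For each data-selected optimal cut-off, including any MAPI cut-point selected under the SAP's Exploratory Aim 2, report bootstrap optimism-corrected SE, SP and Youden index beside the apparent values. Repeat the whole cut-off search in each resample, separately for each AHI threshold. Label these cut-offs exploratory and needing external validation, because in the check above the bootstrap removed only about 70% of the bias. Leave pre-set cut-offs, such as two or more positive Berlin categories, uncorrected.

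The cost is a short extra analysis of data already collected, and secondary figures that look slightly less favourable. Enrolment is complete and the Protocol cites published results, so this is a change to analysis and reporting only.

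### The protocol's Aim 2 rule equates 1 − α* with 94.9%, but with α* = 0.0253 it is 97.47%; 94.9% is the level of a two-sided interval, while the intervals are called one-sided

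*Protocol*

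**What the plan says.** The Aim 2 rule is in the protocol's Statistical Analysis Plan section, in the paragraphs on joint testing of SE and SP. Non-inferiority is tested "by estimating the cross-product of two one-sided" confidence intervals of level 1 − α*. The per-endpoint level is given as "\alpha_{SE} = \alpha_{SP} = \alpha^* = 0.0253", and the protocol says that this choice "ensures that the overall significance region of the joint test of both SE and SP simultaneously remains no greater than" 0.05. The claim is made if the lower confidence limits from both "1 - \alpha^* = 94.9\%$ confidence intervals are strictly above 0.8 for SE and 0.5 for SP". The rule is applied at AHI cut-offs of 5, 15 and 30, overall and in subgroups.

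The protocol's Sample Size Justification repeats the one-sided description. It reports that "214 subjects were available for analysis which yields 83.9% and 98.8% power, respectively". The level behind these powers is given there as 2.53% for each endpoint, with 5% for the joint test.

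The SAP (Aim 2, Hypothesis 2.1) has its own rule: the lower bound of a 95% interval must exceed 80% for SE, and the lower bound for SP must exceed 50%. It does not say whether the intervals are one-sided or two-sided, and it does not mention α*. Its sample sizes assume α = 0.05.

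**The concern.** The equality in the rule is false: no rounding turns 1 − 0.0253 into 94.9%. Neither document calls these intervals two-sided, so the rule can be read in two ways:

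- (a) a one-sided 97.47% lower limit, which tests each endpoint at 2.53%;
- (b) a one-sided 94.9% lower limit, which tests each endpoint at 5.1%.

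An analyst who follows the printed words and the printed percentage arrives at (b), which contradicts the 2.53% stated in two places. This sentence is the protocol's criterion for claiming that the portable study is non-inferior, so a borderline result could be called differently under the two readings. The point concerns only the confidence level printed in the rule, not whether α needed to be split between SE and SP.

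**Working it through.** **Inputs from the protocol.** Overall α = 0.05; α* = 0.0253; null values 0.8 (SE) and 0.5 (SP); assumed true values 0.9 and 0.6; n = 214; printed powers 83.9% and 98.8%. **Assumption.** The documents do not give the split of the 214 into apnea-positive and apnea-negative patients, so prevalences of 30% to 70% are tried. The 30% is the protocol's planning prevalence for Aim 1.

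**1. The level.** α* = 1 − √(1 − 0.05) = 0.0253, so the protocol's α* reproduces. Then:

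- 1 − α* = 1 − 0.0253 = 97.47%
- 1 − 2α* = 1 − 0.0506 = 94.94%, which rounds to the printed 94.9%
- a one-sided 94.9% limit has tail area 1 − 0.949 = 5.1%

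**2. Which level the power statement uses.** Normal-approximation power is Φ[(0.1√n − z√(p0(1 − p0))) / √(p1(1 − p1))], with 0.1√214 = 1.4629.

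- At one-sided 0.0253 (z = 1.9549), SE: (1.4629 − 0.7819)/0.3 = 2.270, power 98.8%. SP: (1.4629 − 0.9774)/0.4899 = 0.991, power 83.9%.
- At one-sided 0.051 (z = 1.6352), SE: (1.4629 − 0.6541)/0.3 = 2.696, power 99.6%. SP: (1.4629 − 0.8176)/0.4899 = 1.317, power 90.6%.

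The two printed values are those for 2.53%, but attached to the opposite endpoints: the protocol gives 83.9% to SE and 98.8% to SP. The formula also uses all 214 patients for each endpoint. Both are separate matters. Here the figures serve only to show which level was used.

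**3. Smallest passing counts, exact (Clopper-Pearson) limits.**

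| Assumed prevalence | SE, (a) | SE, (b) | SP, (a) | SP, (b) | Attained level under (b), SE / SP |
|---|---|---|---|---|---|
| 30% | 58/64 | 57/64 | 88/150 | 86/150 | 4.2% / 4.3% |
| 40% | 77/86 | 76/86 | 76/128 | 74/128 | 3.0% / 4.6% |
| 50% | 94/107 | 93/107 | 65/107 | 63/107 | 4.3% / 4.1% |
| 60% | 112/128 | 111/128 | 53/86 | 52/86 | 3.2% / 3.3% |
| 70% | 130/150 | 129/150 | 41/64 | 40/64 | 3.7% / 3.0% |

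At each split, one SE count moves from fail to pass, and one or two SP counts do. At 30%, 57/64 has a lower limit of 0.788 under (a) and 0.805 under (b); 86/150 has 0.490 and 0.503; 87/150 has 0.497 and 0.510. At 35% (75 positive, 139 negative), 66/75 moves on SE and the attained SE level under (b) is 5.01%.

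**4. Joint coverage.** For two independent one-sided limits: 0.9747² = 95.0% under (a), 0.949² = 90.1% under (b).

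**5. False joint claim.** The claim needs both limits to pass. Its worst-case error rate is therefore the larger of the two single-endpoint levels, reached when the other endpoint passes almost surely. Under (b) that is nominally 5.1%, and 3.3% to 4.6% at the five tabulated splits (5.01% at 35%).

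**6. Chance of success.** At the 30% split with true SE 0.9 and SP 0.6, the chance of claiming non-inferiority is 0.539 × 0.663 = 36% under (a) and 0.692 × 0.774 = 54% under (b).

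**The case against.** The strongest reply is that the text around the equality already fixes the level. α* = 0.0253 stands beside it, the sample-size section repeats 2.53%, and 94.9% is the level of the two-sided interval whose lower end leaves 2.53% in the tail. The rule speaks of lower limits taken from intervals, which fits using the lower end of a two-sided interval. On that view only the label 1 − α* is wrong and every verdict stands. This is probably what was intended. It does not clear the text, because the protocol calls the intervals one-sided in two sections and neither document corrects this.

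A second reply concerns error control. A reader might infer from the 90.1% joint coverage that reading (b) doubles the rate of false non-inferiority claims to about 10%. The documents do not support that. The complement, 9.9%, is the chance that at least one limit misses its true value. The claim requires both limits to pass, so its nominal ceiling is 5.1%, only 0.1 percentage point above 5%. At the five tabulated splits the exact critical counts at 5.1% equal those at 5.0%. This reply stands. What remains under (b) is a mislabelled joint region and a per-endpoint level about twice the stated one.

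Third, a reader might infer that the trial's reported verdict is wrong. Nothing in either document shows that reading (b) was used, and the shifts in step 3 and the contrast in step 6 depend on assumed splits. This also stands.

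**Conclusion.** The printed equality is wrong whatever is assumed: with α* = 0.0253 the one-sided level is 97.47%, and 94.9% belongs to a two-sided interval. Its effect on the analysis is conditional. If the lower limits came from two-sided 94.94% intervals, as the stated 2.53% level suggests, no verdict changes. If one-sided 94.9% limits were used, each endpoint was tested at a nominal 5.1%, and results within one count on SE or one to two on SP would pass where the stated level would fail them. That size rests on exact limits, 214 patients and assumed prevalences of 30% to 70%. The documents support neither a gross inflation of false claims nor a changed trial conclusion. The point still merits correction because it sits in the decision rule, and the SAP's 95% rule, silent on sidedness, does not resolve it: its tail area is 5% if one-sided and 2.5% if two-sided.

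**What to change.** - **Protocol, Statistical Analysis Plan, Aim 2.** Replace the phrase with: one-sided 1 − α* = 97.47% lower confidence limits (equivalently, the lower limits of two-sided 1 − 2α* = 94.94% intervals).
- **SAP, Hypothesis 2.1.** State the sidedness and use the same level, so that the two documents give one rule.
- **Analysis code.** Confirm that the reported lower limits leave 2.53% in the lower tail. If they do, nothing else changes. If they do not, recompute the limits and restate the verdict at each AHI cut-off and in each subgroup.

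The cost is one corrected sentence in each document and a check of one line of code. The only downside arises if one-sided 94.9% limits were used: the reported lower limits would then become slightly lower.
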